First, disruptions from the ongoing COVID-19 pandemic allowed for an unanticipated opportunity to take a preliminary look at the immunologic response in participants in Part A. These data are now available and look extremely promising. Serum from 1 out of 5 participants in the low dose adjuvant group and 3 out of 10 participants in the high dose adjuvant group neutralized BG505/T332N, albeit with low titers (see Figure 4-2 below). This is the first example of vaccine elicited autologous tier 2 neutralization in humans. The internal controls strongly suggest that the neutralizing effect is specific to HIV and not an artifact of the pseudovirus assay because no neutralizing activity against the MLV control virus was detected in the assays with MLV. A major question for HIV vaccinology is whether these neutralization titers can be boosted with a third dose. To test whether this low-tier neutralization could be improved, the protocol was modified to allow participants in Part A an optional third boost. Indeed, 3/5 participants in the 5-mcg dose group had high autologous tier-2 neutralization. The 1-mcg dose group had 1 participant (out of 3) with low-level neutralization, suggesting that the dose of adjuvant may matter.

Second, delays associated with the ongoing COVID-19 pandemic have altered the timelines of anticipated studies such that it is important to understand the role of additional vaccinations with products containing 3M-052 AF. Waiting until Part B is fully enrolled and data is available will take substantially more time (~18 months) as compared to offering participants an additional boost in Part A. The additional boost dose was added to Part A due to a need to evaluate the 3M-052-AF for planned future studies.

Rationale for Adding Part C: Optimization of 3M-052-AF

A third dose of BG505 SOSIP.664 and 3M-052-AF + Alum was offered to participants in Part A (see above). Data from participants who provided additional informed consent are now available and are presented in Figure 4-2.

[figure not shown]

Figure 4-2 Response rate and ID50 neutralizing antibody titers against the autologous tier 2 virus BG505/T332N 2 weeks post second and third vaccination in HVTN 137 Part A.

The high neutralization (with maximum ID50 titers of \sim 8,000) seen in some of the participants in Part A is the first time such high titers have been observed following vaccination in humans (to our knowledge).

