5.2 Objectives and endpoints for Part B

5.2.1 Primary objectives and endpoints for Part B

Primary objective 1:

To evaluate the safety and tolerability of intramuscular (IM) administration of BG505 SOSIP.664 gp140 with the following adjuvants: CpG 1018 + Alum, 3M-052-AF + Alum, GLA-LSQ, or Alum alone

Primary endpoint 1:

Signs and symptoms of local and systemic reactogenicity, laboratory measures of safety, adverse events (AEs), expedited AEs, and AEs of special interest (AESIs)

Primary objective 2:

To evaluate and compare the neutralizing antibody response induced by BG505 SOSIP.664 gp140 with different adjuvants (CpG 1018 + Alum, 3M-052-AF + Alum, GLA-LSQ, or Alum alone)

Primary endpoint 2:

Response rate and magnitude of serum antibody neutralization of autologous (HIV-1 BG505) and other heterologous tier 2 HIV-1 strains as measured by TZM-bl assay 2 weeks after the second and third vaccinations

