6.1 Accrual and sample size calculations

Recruitment will target enrolling 127 healthy, HIV-uninfected adult participants; 115 vaccinees and 12 placebo recipients.

Part A is a dose-escalation study; two doses of the 3M-052-AF adjuvant will be studied in 17 participants (5 vaccinees and 1 placebo in the low-dose group; 10 vaccinees and 1 placebo in the higher dose group). Enrollment to the higher dose group will be triggered when safety in the lower dose group is deemed acceptable. Part B is the adjuvant comparison study; 88 participants will be randomized to one of four groups, with 20 participants randomized to vaccine and 2 to placebo within each group. Section 11.3.2 of the protocol describes the criteria for advancing to Part B based on the Part A data. Part C augments Part B with data on a "medium" dose of the 3M-052 adjuvant (3 mcg as compared to 5 mcg studied in Part B) and with data on a next-generation BG505 trimer (Trimer 4571 versus BG505 SOSIP.664 studied in Part B). The sample-size rationale is described separately for Parts A, B, and C.

Since enrollment is concurrent with receiving the first study vaccination, all participants will provide some safety data. However, for immunogenicity analyses, it is possible that data may be missing for various reasons, such as participants terminating from the study early, problems in shipping specimens, low cell viability of processed PBMCs or high assay background. Immunogenicity data from 17 phase 1 and 2 phase 2a HVTN vaccine trials, which began enrolling after June 2005 (data as of September 2014), indicate that 10% is a reasonable estimate for the rate of missing data at Month 2.5 and 6.5, and 15% is a reasonable estimate at Month 18. For this reason, the sample size calculations in Section 6.1.3 account for 10% and 15% of enrolled participants having missing data for the primary immunogenicity and durability endpoints, respectively.

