6.2 Randomization

A participant's randomization assignment will be computer generated and provided to the HVTN CRS pharmacist through a Web-based randomization

system. For Part A, B and C, participants within each dose group will be randomized to vaccine or placebo assignment. For Part C, Group 7 will be enrolled before Group 8. There will be no randomization for Groups 1 and 2 as they will be enrolled sequentially for dose escalation. At each institution, the pharmacist with primary responsibility for dispensing study products is charged with maintaining security of the treatment assignments (except in emergency situations as specified in the HVTN Manual of Operations [MOP]).

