6.4.4 Immunogenicity analysis

6.4.4.1 General approach

For the statistical analysis of immunogenicity endpoints, data from enrolled participants will be used according to the initial randomization assignment regardless of how many injections they received. Additional analyses may be performed, limited to participants who received all scheduled injections per protocol. Assay results that are unreliable, from specimens collected outside of the visit window, or from HIV-infected participants postinfection are excluded. Since the exact date of HIV infection is unknown, any assay data from blood draws 4 weeks prior to an infected participant's last seronegative sample and thereafter may be excluded. If an HIV-infected participant does not have a seronegative sample postenrollment, then all data from that participant may be excluded from the analysis.

Data from placebo arms will be pooled across groups (n = 8 for analysis in Part B). For analyses of immunogenicity after the second vaccination, data on the 3M-052-AF from Part A (with the MTD of the 3M-052-AF) and Part B will be

pooled. Otherwise, analyses of immunogenicity will be performed separately for Part A and Part B participants.

Discrete categorical assay endpoints (eg, response rates) will be analyzed by tabulating the frequency of positive response for each assay by antigen and treatment arm at each timepoint for which an assessment is performed. Crude response rates will be presented with their corresponding 95% confidence interval estimates calculated using the score test method (84). Because of the small numbers of control participants in each group, no adjustment will be made to the vaccine arm estimates for the false positive rates (FPRs) in the control arms. Barnard or Fisher's exact tests, as specified in the SAP, will be used to compare the response rates of any 2 vaccine arms, with a significant difference declared if the 2-sided p-value is ≤ 0.05 . In general Barnard's is preferred since under most circumstances it is more powerful than Fisher's (85).

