- 3. Withdraw 0.1 mL of CpG 1018 and inject it into an empty sterile vial (mixing vial).
- 4. Withdraw 0.2 mL of Alum and inject into the mixing vial. Mix by gently swirling and inverting the vial about 5 times. Do not shake vigorously. Allow formulation to incubate at room temperature for 30 minutes.
- 5. Withdraw 0.6 mL TBS and inject into the mixing vial. Mix by gently swirling and inverting the vial about 5 times. Do not shake vigorously.

Preparation of BG505 SOSIP.664 gp140:

6. Withdraw 0.1 mL BG505 SOSIP.664 gp140 and add it to the mixing vial. Mix by gently swirling and inverting the vial about 5 times. Do not shake vigorously.

Preparation of the Admixed Vaccine:

- 7. Withdraw 0.5 mL of the mixed preparation for study participant administration. Prior to administration, gently invert the syringe to resuspend admixed product.
- 8. The admixed product is stable for 4 hours at room temperature.

8.3.4 BG505 SOSIP.664 gp140, 100 mcg, admixed with 3M-052-AF, 5 mcg, and Alum, 500 mcg (Group 4)

The highest tolerated dose of 3M-052-AF, 5 mcg, will be used in preparation of study product for administration to Group 4 participants. Follow preparation instructions in Section 8.3.2.

8.3.5 BG505 SOSIP.664 gp140, 100 mcg, admixed with GLA-LSQ, (GLA 5 mcg and QS-21 2 mcg) (Group 5)

For all preparation steps, use a 1 mL Luer-Lok syringe with 0.01 mL graduations and a 22-27 gauge Luer-Lok needle.

- 1. Remove one vial of GLA-LSQ and one vial of TBS from the refrigerator.
- 2. Remove one vial of BG505 SOSIP.664 gp140 from the freezer. Thaw BG505 SOSIP.664 gp140 vial by holding in gloved hand. Once thawed, maintain the vial in upright position and gently swirl or tap the vial to mix the contents. Do not invert the vial.

Preparation of BG505 SOSIP.664 gp140:

- 3. Withdraw 0.8 mL of TBS and inject it into an empty sterile vial (mixing vial).
- 4. Withdraw 0.2 mL BG505 SOSIP.664 gp140 and add it to the mixing vial. Mix by gently swirling and inverting the vial about 5 times. Do not shake vigorously.

Preparation of the Admixed Vaccine:

- 5. Withdraw 0.4 mL of the mixed preparation and add to GLA-LSQ vial. Mix by gently swirling and inverting the vial about 5 times. Do not shake vigorously.
- 6. Withdraw 0.5 mL of the mixed preparation for study participant administration. To maintain study blind, wait 30 minutes prior to study product delivery to clinic staff. Prior to administration, gently invert the syringe to resuspend admixed product.

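### Pooling ten Part A recipients into the Part B 3M-052-AF arm after dose 2 puts about a third of that arm outside the randomised comparison at a primary timepoint

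*Protocol*

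**What the plan says.** Section 6.4.4.1 of the protocol pools Part A and Part B data on the selected 3M-052-AF dose: "For analyses of immunogenicity after the second vaccination, data on the 3M-052-AF from Part A (with the MTD of the 3M-052-AF) and Part B" are combined. It then adds: "Otherwise, analyses of immunogenicity will be performed separately for Part A and Part B participants". The separate analysis is therefore the rule everywhere except after dose 2, and no Part-B-only analysis is named for that timepoint.

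The timepoint is a primary one. The second primary endpoint of Part B (Section 5.2.1) is neutralisation "as measured by TZM-bl assay 2 weeks after the second and third vaccinations", and the objective is to compare four adjuvants. Section 6.1 describes the randomised design: "88 participants will be randomized to one of four groups, with 20 participants randomized to vaccine and 2 to placebo within each group".

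The pooled Part A participants are Group 2. Section 6.1 gives that group as "10 vaccinees and 1 placebo in the higher dose group", and Section 8.3.4 identifies the dose: "The highest tolerated dose of 3M-052-AF, 5 mcg, will be used in preparation of study product for administration to Group 4 participants". On allocation, Section 6.2 says: "There will be no randomization for Groups 1 and 2 as they will be enrolled sequentially for dose escalation". Within each group, participants were randomised to vaccine or placebo.

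Section 4.2.2 reports that Part A data were examined early and that "3 out of 10 participants in the high dose adjuvant group neutralized BG505/T332N". Appendix W sets a target of Day 56 for the second vaccination in both parts, with an upper allowable window of +180 days in Part A and +14 days in Part B.

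**The concern.** Part B exists to compare adjuvants under randomisation. The pooling rule adds participants to one of its four arms only, and those participants had no chance of being assigned CpG 1018, GLA-LSQ or Alum alone. Any difference between the parts, such as enrolment period or the interval between the first two doses, then enters the 3M-052-AF contrasts as if it were an adjuvant effect. Section 6.4.4.1 itself says that data are to be used by initial randomisation assignment, which fits poorly with bringing in participants who were never assigned among the adjuvants.

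The added data are also partly known. With 3/10 fixed in advance, part of the primary result for one arm was on record before Part B reported.

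**Working it through.** **The plan's own figures.** Table 6-6 gives 81% power for a 1.0 SD difference with 18 per arm (one-sided 0.025 Wilcoxon). Simulation with 4,000 runs gives 80.5%. Section 6.1.3 gives 97% power for response rates of 50% vs 100% with 18 per arm (Fisher). Exact enumeration gives 98.5%. Both agree with the plan to within 2 points, and both use Part B numbers alone, so the planned sample size does not depend on pooling.

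**Share of the arm.** Section 6.1.3 allows for 18 evaluable participants of 20 per Part B arm. Part A adds 10, all with a reported neutralisation result. The share is 10/(18 + 10) = 10/28 = 36% (10/30 = 33% of those enrolled).

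**Permitted timing of dose 2 (Appendix W).** Part A: 56 + 180 = Day 236. Part B: 56 + 14 = Day 70. The earliest target day is 56 − 7 = Day 49 in both. The Part A sample after dose 2 is timed from dose 2, so a late second dose does not make that sample out of window.

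**Contrasts affected.** Four vaccine arms give 6 pairs, of which 3 involve 3M-052-AF. Its contrast with placebo is also affected. The other 3 pairs and all analyses after dose 3 are not.

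**Bias in the response rate.** Hold Part A at 3/10 and let p be the true Part B rate in the 3M-052-AF arm. The expected pooled rate is (3 + 18p)/28, so the bias is (3 + 18p)/28 − p. With the comparator rate also equal to p, exact enumeration gives the chance that a two-sided 0.05 Fisher test rejects:

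| p | Pooled rate | Bias (points) | Rejection, pooled | Rejection, Part B only |
|---|---|---|---|---|
| 10% | 17.1% | +7 | 1.5% | 0.9% |
| 30% | 30.0% | 0 | 2.2% | 2.2% |
| 50% | 42.9% | −7 | 4.1% | 2.9% |
| 70% | 55.7% | −14 | 9.6% | 2.2% |
| 80% | 62.1% | −18 | 17.6% | 2.0% |

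**Loss of a real difference.** If the true Part B rates are 71% (3M-052-AF) and 20% (comparator), Fisher power is 85% with Part B only and 66% after adding the fixed 3/10.

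**One worked table.** Suppose Part B gives 13/18 (72%) vs 6/18 (33%). Adding 3/10 gives (13 + 3)/(18 + 10) = 16/28 (57%) vs 6/18.

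| Data | Fisher p | Barnard p |
|---|---|---|
| Part B only, 13/18 vs 6/18 | 0.044 | 0.029 |
| Pooled, 16/28 vs 6/18 | 0.141 | 0.128 |

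The conclusion changes under both tests that Section 6.4.4.1 allows.

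**Magnitude.** If Part A responses differ from Part B by 0.5 SD (an assumed figure) and the Part B arms do not differ, two-sided Wilcoxon type I error is about 8%. At 1.0 SD it is about 16%. With no shift it is about 4%.

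**The case against.** Pooling has a rationale. Group 2 and Group 4 receive the same antigen, adjuvant dose and preparation under the same eligibility criteria, with the same target day for dose 2. If the parts are exchangeable, nominal power for a 1.0 SD difference rises from about 81% to about 88%. This is also a phase 1 trial that states it has limited power to compare response rates, the adjuvant ranking in Table 6-7 is set at Month 6.5, and no decision in the protocol hangs on the contrast after dose 2. These points stand, and they are why this is a should-fix.

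A reader might also infer more than the documents support:

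- That pooling undoes the randomisation of Part B as a whole. It touches three of six vaccine pairs and one placebo contrast, at one of two primary timepoints.
- That Part A second doses were in fact given months late. Day 236 is only the permitted limit, and the available text gives no actual intervals. If +180 were read as study day 180, the limit would be about 6 months.
- That pooling was chosen because of the 3/10 result. The rule is worded generically in terms of a maximum tolerated dose, which suggests that it predates dose selection, and the version history lists no change to it.
- That pooling favours 3M-052-AF. A table such as 4/18 vs 0/18 moves from Fisher p = 0.104 to 0.032 (7/28 vs 0/18), but under Barnard's test, which the protocol generally prefers, it is already significant at 0.038 and moves to 0.022. Much of the Fisher change comes from the larger n: the rate moves only from 22% to 25%.
- That sites differed between the parts. The protocol does not document this.

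**Conclusion.** The concern holds for the 3M-052-AF contrasts at Month 2.5. As written, the only analysis named there takes about 36% of one arm from participants who were not randomised among adjuvants, were enrolled earlier under a wider dose-interval window, and whose neutralisation result was already known.

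The size and direction of the bias cannot be fixed from the protocol, because they depend on the Part B response rates. Near 30% there is none. At 10% the pooled rate is about 7 points too high, though false rejection stays low at 1.5%. At 70–80% it is 14 to 18 points too low and false rejection reaches about 10–18%. Those high rates are an assumption well above the 3/10 seen in Part A. The calculations assume 18 evaluable participants per Part B arm and all 10 from Part A. Severity: should-fix.

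**What to change.** Replace the pooling sentence in Section 6.4.4.1 with a statement that between-arm comparisons of immunogenicity at Month 2.5 use randomised Part B participants only. Report the combined Part A and Part B 3M-052-AF estimate as supportive and descriptive, with the actual intervals between the first two doses shown. Limiting that supportive estimate to Part A participants dosed inside the Part B window is not needed, and it could leave a very small subset.

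The cost is one sentence, plus the nominal precision gained by pooling in the main comparison. The 3M-052-AF arm falls from about 28 to about 18 at this timepoint, which is the size that Tables 6-5 and 6-6 already assume, so no power stated in the protocol is lost.

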The protocol team therefore desires to build on these exciting results with a goal of optimizing the 3M-052 AF + Alum for advancement of this product.

Using the same schedule, we propose to determine whether a 3-mcg dose of 3M-052 AF + Alum is sufficient to drive tier 2 autologous neutralization with less systemic reactogenicity than observed with the 5-mcg dose.

Additionally, we propose to test whether the VRC trimer 4571 adjuvanted with 3M-052 AF leads to the development of tier 2 (both autologous and heterologous) neutralizing antibodies. The VRC 4571 trimer is a stabilized BG505 trimer designed to better elicit nAbs. The VRC trimer 4571 was formulated in Alum in a recent VRC phase 1 trial, but no autologous nAbs were elicited. This trial used Alum as an adjuvant. To test whether there is a conceptual issue with trimer design or, alternatively, whether the adjuvant is a critical mediator for neutralization, we proposed to add an arm testing whether VRC 4571 leads to

neutralization of the autologous and other tier 2 viruses. This is a critical question for the field because it will determine whether the conceptual framework (that alterations in the stabilization of a trimer will lead to improved neutralization) is accurate.

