If a substantial amount of immunogenicity data are missing for an endpoint (at least 1 value missing from more than 20% of participants), then using the methods that require the MCAR assumption may give misleading results. In this situation, analyses of the immunogenicity endpoints at a specific timepoint will be performed using parametric generalized linear models fit by maximum likelihood. These methods provide unbiased estimation and inferences under the parametric modeling assumptions and the assumption that the missing data are missing at random (MAR). MAR assumes that the probability of an observation being missing may depend upon the observed responses and upon observed covariates, but not upon any unobserved factors. Generalized linear models for response rates will use a binomial error distribution and for quantitative endpoints, a normal error distribution. For evaluating repeated immunogenicity measurements over time, linear mixed effects models will be used. If the immunological outcomes are left- and/or right- censored, then the linear mixed effects models of Hughes (90) will be used, because they accommodate the censoring. In addition, secondary

analyses of repeated immunogenicity measurements may be done using weighted generalized estimating equation (GEE) (91) methods, which are valid under MAR. All of the models described above in this paragraph will include as covariates all available baseline predictors of the missing outcomes.

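### The single-timepoint GLM fallback for more than 20% missing data is called unbiased under MAR, but from Month 6.5 on it cannot use earlier responses, so the claim holds only for missingness explained by baseline covariates

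*Protocol*

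**What the plan says.** Protocol section 6.4.4.1 uses complete-case methods when little is missing and says that they need data missing completely at random. The fallback starts when an endpoint has "at least 1 value missing from more than 20% of participants". Then "analyses of the immunogenicity endpoints at a specific timepoint will be performed using parametric generalized linear models fit by maximum likelihood". The claim made for it is "These methods provide unbiased estimation and inferences under the parametric modeling assumptions", together with MAR, and "MAR assumes that the probability of an observation being missing may depend upon the observed responses and upon observed covariates". The models are to "include as covariates all available baseline predictors of the missing outcomes". "Generalized linear models for response rates will use a binomial error distribution", with a normal error for quantitative endpoints; no link function or test statistic is named.

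The same paragraph assigns linear mixed models to measurements evaluated over time, in a censored form where outcomes are left- or right-censored. Weighted GEE is an optional secondary analysis of repeated measurements.

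On expected loss, section 6.1 gives 10% at Months 2.5 and 6.5, and "15% is a reasonable estimate at Month 18". Section 6.1.3 applies 15% at Months 12 and 18.

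**The concern.** The fallback exists because complete-case analysis may mislead once much is missing. But a participant whose only modelled outcome is missing adds nothing to the likelihood of a one-timepoint GLM. The replacement is therefore another complete-case analysis, with baseline adjustment. It is valid if missingness depends on the covariates in the model. It is not valid in general if missingness depends on an earlier observed response, which the protocol's own definition of MAR allows.

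Both Month 2.5 and Month 6.5 are primary neutralization timepoints (section 5.2.1), so an earlier response is available for the later one, and likewise for the durability visits. At stake is that a report could cite the protocol's sentence as assurance that adjuvant contrasts are protected when part of the MAR problem is untouched.

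**Working it through.** **1. Planning figures.** 20 × 0.90 = 18 and 20 × 0.85 = 17 per arm, as in section 6.1.3. The fallback paragraph states no computed figure of its own.

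**2. Does planned loss reach the trigger?** The rule is per endpoint, so the visits to count are those in each endpoint's definition (sections 5.2.1 and 5.2.2). The lower bound assumes nested loss (the largest single rate); the upper assumes independent loss.

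| Endpoint (Part B) | Visits, months | Nested | Independent |
|---|---|---|---|
| Primary neutralization | 2.5, 6.5 | 10% | 1 − 0.90² = 19% |
| Neutralization durability | 12, 18 | 15% | 1 − 0.85² = 28% |
| Binding antibody, memory B cells, ICS | 2.5, 6.5, 12, 18 | 15% | 1 − 0.90² × 0.85² = 41% |

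**3. Error in an arm mean.** The protocol gives neither the correlation between visits nor a missingness mechanism, so both are assumed. A standard-normal Month 2.5 response Y1 has correlation 0.3 with a baseline covariate; the Month 6.5 response is Y2 = ρ·Y1 + √(1 − ρ²)·noise, with true mean 0. Missingness is logit P(Y2 missing) = a − s·Y1, with a set to give 25%. There were at least one million simulated participants per arm, so the figures are bias, not sampling error.

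| ρ | s | Raw complete-case mean | Baseline-adjusted GLM | Also using Y1 |
|---|---|---|---|---|
| 0.5 | 0.5 | 0.060 | 0.055 | 0.000 |
| 0.5 | 2 | 0.158 | 0.147 | −0.001 |
| 0.7 | 1 | 0.150 | 0.138 | 0.001 |
| 0.9 | 0.5 | 0.106 | 0.097 | −0.001 |
| 0.9 | 2 | 0.287 | 0.268 | 0.001 |

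Over the full grid the error runs from 0.06 to 0.29 SD unadjusted and from 0.06 to 0.27 SD with baseline adjustment. As a control, when missingness depends only on the modelled baseline covariate, the raw mean is off by 0.105 and the GLM by 0.000.

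**4. Error in the arm contrast (ρ = 0.7; s = 0.5, 1, 2).**
- Dependence in one arm only, true difference 0: 0.08, 0.13, 0.20 SD; log odds ratio of response 0.12, 0.23, 0.34.
- Same mechanism in both arms, true difference 0: 0.00.
- Same mechanism in both arms, true difference 1.0 SD: 0.97, 0.92, 0.83 SD.
- Using each arm's Month 2.5 responses returns 0.00 and 1.00.

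**5. Arms at 0% or 100%.** For 0/15 against 8/15 with a logit link (assumed), the estimate diverges: software prints 22.7 with standard error 12,444 and Wald p = 0.9985. From the same model the likelihood-ratio p is 0.0002, the score p is 0.001, and the profile 95% lower limit of the log odds ratio is 1.90; Fisher p is 0.002. In very small samples the likelihood-ratio test can be liberal: 0/7 against 3/7 gives 0.026, Fisher 0.19. The 50% versus 100% scenario in section 6.1.3 also has a boundary arm. Its stated power of 97% is close to what I obtain (98.5% by Fisher enumeration, 96.7% by normal approximation).

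**The case against.** **The mechanism may be remote.** Assay results are not given to participants or medical professionals (section 10.1), and Part B participants and site staff are blinded to group (section 6.3). The listed causes of loss are early termination, shipping, cell viability and assay background. If planned loss of 10% were entirely titre-driven in one arm (20% below the median, none above), the bias is about 0.06 SD and type I error 5.6%. This stands as a limit on size. It does not make the sentence correct.

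**The sentence is right for covariate-dependent missingness**, and the MAR definition also serves the mixed models beside it. That is true, and Month 2.5 is unaffected because Appendix P schedules no neutralization draw between Day 0 and Day 70. For later visits, though, the claim is attached to the single-timepoint models, and the methods that would use earlier responses are not assigned to that contrast.

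**Stronger readings that a reader might infer:**
- *The binomial model cannot test against an arm with no responders.* It can: likelihood-ratio and score tests work, and the protocol does not prescribe Wald.
- *A zero-responder Alum arm is to be expected.* Section 4.2.2 reports of Trimer 4571 in Alum that the trial ran "but no autologous nAbs were elicited", but that is a different trimer from the Part B Alum arm. For BG505 SOSIP.664, section 4.1.1 expects responses in up to 50% of recipients.
- *The assay floor is ignored.* The sentence on censored outcomes can be read as covering it.
- *Four in ten participants trip the trigger for the primary contrast.* The 41% fits only four-visit endpoints with independent loss.

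**Conclusion.** The concern holds in a limited form. For Month 6.5 and later, the claim of unbiasedness is broader than the method supports. It is true if missingness depends on the modelled baseline covariates, and not in general if it depends on an earlier observed response. Under the assumed correlations, slopes and 25% loss, an arm mean errs by about 0.06 to 0.29 SD. Bias in a null contrast needs a mechanism that differs between arms; a common one shrinks a true 1.0 SD difference to between 0.97 and 0.83 SD.

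The fallback is within reach at planned loss for neutralization durability and for four-visit endpoints. For primary neutralization it needs loss worse than planned. The boundary-arm point is secondary: there is no finite odds ratio and no usable Wald inference when an arm has 0% or 100% responders, but response rates can still be estimated and compared.

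**What to change.** - In this fallback, take single-timepoint titre contrasts from the repeated-measures mixed-effects model already cited, in its censored form where needed, fitted to all observed visits.
- For response rates, use multiple imputation or inverse-probability weighting that includes earlier responses. Do not simply add the Month 2.5 response as a covariate in the arm comparison: vaccination affects it, so that would change the contrast being estimated.
- Limit the sentence on unbiasedness to missingness that depends on covariates in the model, or attach it to the methods above.
- For arms with 0% or 100% responders, keep the exact tests of the general approach, or name Firth or profile-likelihood inference.

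The cost is a few sentences of protocol or SAP wording and modest programming. No new data, visits or sample size are needed.
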